10.4.2. Secondary and Exploratory Efficacy Endpoints

The same approach as used for the primary efficacy endpoint will be applied for secondary and exploratory endpoints that are categorical in nature.

Changes from baseline in PBMC ELISpot, HBsAg, HBcrAg, pg-RNA, and quantitative HBV DNA will be analyzed using a mixed model for repeated measures (MMRM). The model will include the fixed effects of treatment, stratification factor, week, and treatment-by-visit interaction as well as the continuous, covariate of baseline level. The model will employ an unstructured within patient covariance matrix and a restricted maximum likelihood (ReML) estimation method.

Relationships between hepatitis flares and HBsAg loss and/or decline will be evaluated logistic and linear regression.

A Kaplan-Meier model will be developed to compare changes between treatment groups in HBsAg clearance and a 1-log reduction in HBsAg over time.

No multiplicity adjustments will be made for secondary or exploratory endpoints.

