2. INTRODUCTION

An interim analysis was conducted at Week 24 that demonstrated that the primary and secondary endpoints of the study were not met. HepTcell was well-tolerated, with no significant safety events.

Per protocol Section 7.2, the Sponsor is terminating the study for lack of efficacy. The IND and respective CTAs will be inactivated, and the investigational product will not undergo further clinical testing. As there were no ongoing MAEs, NCIs or IMCs at the time of termination, safety follow-up will end as of this date. Any accrued efficacy or safety information prior to study termination will be provided in tables and listings only up through the date of study termination.

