4.2.2 Secondary Efficacy Endpoint

Proportion of patients achieving serologic clearance of HBsAg on Day 169

A patient is considered to have achieved serologic clearance of HBsAg on Day 169, if HBsAg on Day 169 is below the limit of quantitation (defined as 0.05 IU/mL).

Proportion of patients achieving serologic clearance of HBV DNA on Day 169

A patient is considered to have achieved serologic clearance of HBV DNA (PCR) on Day 169, if HBV DNA (PCR) on Day 169 is below the limit of quantitation (defined as 10 IU/mL).

Changes in qHBsAg, HBV DNA, HBcrAg and pg-RNA levels, Baseline to Days 85 and 169
 Changes in qHBsAg, HBV DNA, HBcrAg and pg-RNA levels from Baseline to Days 85 and 169
 are defined as:

Change of Test from Baseline to Day 85 = Test value [Day 85] – Test value [Baseline];

Change of Test from Baseline to Day 169 = Test value [Day 169] – Test value [Baseline];

where Test correspond to the following quantitative tests:

qHBsAg, HBV DNA and HBV DNA log, HBcrAg (Log U/mL and kU/mL) and pg-RNA

• Change in LPMIX9 IFN-γ Spot Forming Cells (SFC) by ELISpot assay in PBMCs, Baseline to Days 85 and 169

Change in LPMIX9 IFN-γ SFC by ELISpot assay in PBMCs, Baseline to Days 85 and 169 are defined as:

Change of LPMIX9 IFN-γ SFC from Baseline to Day 85 = LPMIX9 IFN-γ SFC [Day 85] – LPMIX9 IFN-γ SFC [Baseline];

Change of LPMIX9 IFN-γ SFC from Baseline to Day 169 = LPMIX9 IFN-γ SFC [Day 169] – LPMIX9 IFN-γ SFC [Baseline]

Where LPMIX9 is a pool of the 9 peptides contained in FP-02.2. Values for analyses are LPMIX9 raw values corrected with the control.

- Change in LPMIX9 IFN-γ Spot Forming Cells (SFC) by ELISpot assay in PBMCs:
 - Some replicates of some subjects and days, the -ve Control was higher than the analogous LPMIX9 value which led to negative values.
 - Given that the control does not correspond to the analogous LPMIX9 in each of the replicates since the corresponding wells are not linked, the calculation of the continuous parameter to be analyzed, will be revised as follows:
 - Mean (i=1,2,3) of ["Value for Peptide LPMIX9 (R#i)"] Mean (i=1,2,3) of ["-ve Control for Peptide LPMIX9 (R#i)"] where R#i is replicate #i, i=1,2,3
 - Adding a new specification: If the result turns out negative, it will round up to "0"

Please refer to section 5.3.2 for details on the handling of intercurrent events and missing data or all the secondary endpoints.

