Changes from baseline for IFN- γ frequency by ELISpot assay in PBMCs levels (including LPMIX9 IFN- γ SFC a) will also be analyzed fitting a mixed model for repeated measures (MMRM) including treatment group, visits days (Day 1 through Day 169), and baseline values as a covariate. Interactions between visit days and treatment group will also be included. The model will employ an unstructured within patient covariance matrix and a restricted maximum likelihood (ReML) estimation method. The data distribution will be tested for normality and appropriate transformations will be applied, as needed. Any transformation, if applied, will be reported.

Change from baseline is calculated only for patients with non-missing values for both the baseline and the time-point of interest and will be missing otherwise.

- The LPMIX9 variable is not normally distributed, and none of the transformations we have attempted are valid.
 - Upon examining the data, highly right-skewed distribution was observed, with a significant number of subjects reporting a value of 0.
 - Given these challenges we cannot proceed the Mixed model proposed the previous version of SAP because the data do not fit the assumptions of normality. Therefore, the Wilcoxon-Mann Whitney test to compare these differences between treatments will be used instead.

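### ELISpot was moved to an unadjusted Wilcoxon test on changes; a baseline-adjusted rank analysis beside it would keep the robustness and usually gain power

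*SAP*

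**What the plan says.** Protocol 10.4.2 analyses change in PBMC ELISpot with a mixed model for repeated measures. Its terms include treatment, visit and their interaction, "as well as the continuous, covariate of baseline level".

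SAP 5.3.2.2.4 still prints a model of that kind, with "visits days (Day 1 through Day 169), and baseline values as a covariate". The same section then says of the LPMIX9 variable that a "highly right-skewed distribution was observed, with a significant number of subjects reporting a value of 0", and that "none of the transformations we have attempted are valid". It concludes: "Therefore, the Wilcoxon-Mann Whitney test to compare these differences between treatments will be used instead". No covariate, stratification or other use of baseline is named for the new test, and Table 14.2.2.4.2 in SAP Appendix 1 is titled as a non-parametric model.

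Two data rules matter here:

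- SAP 5.3.2.2.4: "Change from baseline is calculated only for patients with non-missing values for both the baseline and the time-point of interest". The tested quantity is therefore follow-up minus baseline.
- SAP 4.2.2, on the background-corrected count: "If the result turns out negative, it will round up to" zero. The scale therefore has a hard floor.

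The SAP history dates the non-parametric model to version 2.0 (22-Apr-2024). Section 2 of that version also states: "An interim analysis was conducted at Week 24 that demonstrated that the primary and secondary endpoints of the study were not met". Section 5.3.17, which is meant to list departures from the protocol's analyses, mentions only the ECG parameters.

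**The concern.** Non-normality is a reason to stop using a normal-theory model. It does not bear on whether to adjust for baseline, because rank ANCOVA and proportional-odds models need no normality and keep the baseline term. The SAP considers neither.

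Baseline is likely to matter for this variable. A patient who starts at the floor of zero cannot fall, while one who starts high can fall a long way through regression to the mean. The rank of a patient's change therefore depends partly on the starting value, and an unadjusted test treats that part as noise.

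Cellular immune response is a stated secondary objective. If an adjusted analysis of the same samples would be more sensitive, a non-significant Wilcoxon result is weaker evidence of no immune effect than the trial could provide.

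**Working it through.** **The plan's own figure.** No power, SD, correlation, zero share or effect size is given for ELISpot. The only power statement (Protocol 10.2, SAP 5.1) is for the primary endpoint: 40 per arm, 3% v 25%, two-sided 0.05, about 80%. It reproduces: exact power of Fisher's test is 78.0%, and the pooled normal approximation gives 82.2%. It serves here only as the source of n = 40 per arm.

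**Normal-theory guide.** With equal variances at baseline and follow-up and correlation r, the treatment contrast has variance proportional to 2(1 − r) for a change score and 1 − r² for baseline-adjusted ANCOVA. The relative efficiency of the change score is

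(1 − r²) / [2(1 − r)] = (1 + r)/2,

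which is 0.65, 0.75 and 0.85 at r = 0.3, 0.5 and 0.7. If ANCOVA has 80% power, the change score has Φ(√RE × 2.80 − 1.96) = 62%, 68% and 73%. These data are not normal, so this shows direction only.

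**Simulation on data of the described shape.**

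- Inputs from the documents: 40 per arm, 1:1, right skew, many zeros, two-sided 0.05.
- Assumed inputs: latent bivariate normal values with correlation r; zero below a cut that gives 30% or 50% zeros; exponential above it with log-scale SD 1.0 or 1.5; a latent shift of 0.6 SD in the treated arm; one post-baseline visit.
- Runs: 2,000 per scenario for power and 1,500 under the null.
- Tests: linear ANCOVA on raw change (a single-visit stand-in for the mixed model), Wilcoxon on change, and rank ANCOVA (ranks of follow-up on ranks of baseline plus treatment).

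Power, as the range over the four zero-share and skew settings:

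| r | Linear ANCOVA | Wilcoxon on change | Rank ANCOVA | Rank ANCOVA minus Wilcoxon (points) |
|---|---|---|---|---|
| 0.3 | 41-61% | 55-60% | 71-76% | 16.0 to 18.8 |
| 0.5 | 45-68% | 67-73% | 78-83% | 9.5 to 12.9 |
| 0.7 | 55-79% | 84-89% | 88-92% | 2.6 to 3.9 |
| 0.85 | 73-94% | 97-99% | 97-99% | −0.6 to 0.6 |

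One line in full (30% zeros, SD 1.5, r = 0.5): linear 46.3%, Wilcoxon 70.2%, rank ANCOVA 83.1%, so the gain over Wilcoxon is 83.1 − 70.2 = 12.9 points.

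Null rejection was 4.1-6.3% for Wilcoxon and 4.1-5.9% for rank ANCOVA. The Monte Carlo standard error is about 1 point for power near 70% (√(0.7 × 0.3/2000) = 0.010) and about 0.6 points for the null rates.

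Further runs of the same design gave 83-87% v 89-92% at r = 0.7, so the gain there is stated as 3-6 points.

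**A different form of effect.** With 40% zeros and 20 scenarios, half using a latent shift and half an additive effect confined to a 40% responder subset, rank ANCOVA exceeded Wilcoxon on change in all 20, by near 0 to 24 points.

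**Wilcoxon against the linear adjusted model.** In the 16 table scenarios Wilcoxon had the higher power in 14. The exceptions were both at r = 0.3 and SD 1.0 (59.6% v 61.2%, and 54.6% v 59.9%). Under the responder-subset effect, Wilcoxon won all five scenarios at SD 1.5 and lost all five at SD 1.0.

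**The case against.** The strongest case on the other side has four parts.

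**The switch is permitted and largely disclosed.** Protocol 10.6 lets the SAP supersede non-primary analyses. The version history names the new model, section 5.3.2.2.4 gives the reason, and the table is retitled. This stands. What is missing is the entry in 5.3.17 and the removal of the old model text for LPMIX9.

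**The size of the gain rests on unseen inputs.** This also stands. At high correlation there is almost nothing to gain.

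**A new main test chosen now would be a second choice made after the data, and one picked for power.** This stands too, and it is why the adjusted analysis should sit beside the Wilcoxon test and not displace it. A related objection is that ranking the follow-up value departs from an endpoint defined as change. That carries less weight: in a linear model with a baseline covariate, the treatment coefficient is the same whether the outcome is the value or the change. The rank version is not identical but keeps the same adjusted comparison.

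**The stakes are limited.** SAP 5.3 calls the study exploratory, multiplicity is not controlled, and SAP section 2 says the study is being terminated for lack of efficacy. No decision in the documents depends on this p-value.

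A reader might also infer three stronger things that the documents do not support:

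- *That baseline was discarded.* It is subtracted; only the covariate adjustment is lost.
- *That power was lost against the mixed model.* Under a latent shift, Wilcoxon usually beats a linear adjusted model on data of this shape. Under other effects the direction varies.
- *That the test was picked with treatment codes in view.* The version that carries the switch also reports the Week 24 result, but the documents do not say whether the inspection of the ELISpot data was unblinded, or which test the interim analysis used.

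**Conclusion.** The point holds in a limited form. Leaving the normal-theory model was justified. Dropping the planned baseline adjustment was not explained, and the stated reason does not cover it.

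Against Wilcoxon on change, a baseline-adjusted rank analysis gains about 16-19 points of power at a correlation of 0.3, 10-13 at 0.5 and 3-6 at 0.7, with near 0 at 0.85, at the same type I error. These figures assume 40 evaluable patients per arm, 30-50% zeros, one visit, and a latent shift of 0.6 SD. The correlation is on the latent scale. The observed baseline and Day 85 or Day 169 values would show where the trial lies.

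The single-visit simulation does not measure the mixed model's joint use of both visits or its handling of missing values. The Wilcoxon test gives these up, and a visit-by-visit rank ANCOVA does not restore them.

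The consequence is for interpretation: a null Wilcoxon result alone should not be read as the best evidence these samples can give on the cellular-immunity objective.

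**What to change.** In SAP 5.3.2.2.4, at Days 85 and 169, add rank ANCOVA (ranks of the post-baseline value on ranks of baseline plus treatment) or a proportional-odds model with baseline as a covariate. Name one of them in advance. Report it beside the Wilcoxon test, show both results whatever they are, and label both as post hoc, since both follow inspection of the data.

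Remove the superseded mixed-model paragraph for LPMIX9, and record the switch and its reason in 5.3.17.

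The cost is a few sentences and one extra procedure per visit on data already collected. The drawback is that a rank-scale estimate is less direct to interpret, although the Wilcoxon test as written specifies no effect estimate either.

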5.3.3 Safety Analyses

Summary statistics will be provided by treatment arm and overall (if applicable) for the safety endpoints; summaries will be provided on the Safety population. Listings will also be presented.

The safety endpoints will be considered as described in section 4.3. Analyses to be performed are described in the following subsections.

5.3.3.1 Treatment exposure

Patients are initially planned to receive 6 doses of HepTcell or placebo at study visits 4 weeks apart (Days 1, 29, 57, 85, 113, 141). A sentinel cohort of 12 patients (6 receiving HepTcell and 6 placebo) will undergo blinded safety review by the Safety Committee 7 to 10 days after all ongoing patients in the sentinel cohort have completed the respective dose of study medication and will determine the decision to continue at that dose to the expanded cohort.

Exposure to the investigational product (HepTcell or placebo) will be summarized by descriptive statistics by treatment arm and dose (expressing cumulative data with previous doses) number as follows:

- Number of patients under each dose number
- Total number of doses administered
- Duration of exposure (defined as "last dose date of study drug first dose date of study drug +
 1", regardless of temporary interruptions in study drug administration and will be expressed in
 days)

A listing of investigational product administration data by day of administration will be provided.

Randomization number assignment along with data related as well as cohort of assignment will be listed.

5.3.3.2 Adverse events

AEs will be coded using MedDRA v25.1 or subsequent.

Summary of AEs:

The primary focus of AE reporting will be on Treatment-Emergent Adverse Events (TEAEs). A TEAE is defined as an AE that starts or worsens on or after the date and time of the first administration of the study drug.

All reported AEs (regardless of TEAE or not) will be included in a by-patient AE listing, identifying which is treatment emergent and which it not.

If an AE date/time of onset (occurrence, worsening, or becoming serious) is incomplete, an imputation algorithm will be used to classify the AE as treatment-emergent or not. The algorithm for imputing date/time of onset will be conservative and will classify an AE as treatment-emergent unless there is definitive information to determine it is pre-treatment or post-treatment. Details on classification of AEs with missing or partial-onset dates are provided in Section 5.3.9.

AE summaries will include number (n) and percentage (%) of patients experiencing an AE within each treatment arm and overall if appropriate. The denominator for computation of percentages is the number of patients in the safety population within each treatment arm. The number of events will be included in some summaries as well whenever appropriate.

Unless otherwise specified, when applicable, sorting order will be by decreasing number of patients in PTs within SOCs based on total patients. When more than one PT has same number of patients, the order of presentation will be alphabetical in PTs.

Multiple occurrences of the same event in the same patient will be counted only once for patients counting in the tables within a treatment arm.

Summary of All TEAEs:

The following TEAE summaries will be generated for the safety population:

- An overview of TEAEs. Number (%) of patients will be provided by treatment arm, to include:
 - o TEAEs.
 - o MAEs.
 - o Grade 3 (Severe), Grade 4 (Life-threatening), and Grade 5 (Fatal) TEAEs.
 - Serious TEAEs.
 - Treatment-related AEs (defined as those events other than 'Unrelated/Unlikely related' as assessed by the investigator).
 - TEAEs serious leading to death.
 - TEAEs leading to study drug permanent discontinuation.

22-Apr-2024

- TEAEs leading to clinical management of the AE.
- All TEAEs by primary SOC and PT.
- All TEAEs presented by PT.
- All treatment-related AEs presented by primary SOC and PT.
- All treatment-related AEs Grade 3 or higher, presented by primary SOC and PT.
- All TEAEs by maximum severity (i.e., Grade 1, Grade 2, Grades 3 to 5), presented by primary SOC and PT.

Separate listings will be provided for TEAEs leading to premature study drug discontinuation/interruption and Study-Drug-Related TEAEs

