3.4. Safety Endpoints

- Incidence and severity of AEs, medically-attended AEs (MAEs), new-onset chronic illnesses (NCIs), and immune-mediated medical conditions (IMCs)
- Incidence and severity of local and systemic reactogenicity events
- Incidence and duration of hepatitis flares, defined as alanine aminotransferase (ALT) \geq 3 × upper limit of normal (ULN) and \geq 100 U/L
- Changes in ALT, aspartate aminotransferase (AST), alkaline phosphatase (AP), gamma glutamyl transferase (GGT), bilirubin total and direct, international normalized ratio (INR) and other laboratory parameters

Safety endpoints will be assessed separately for the 24-week Treatment Period and 52-week Follow-Up Period.

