- 1 If an authorized COVID-19 vaccine has been administered in proximity to a scheduled IP administration, a ± 3 day window is allowed for IP dosing.
- ^m After Day 169 or ET, only MAEs, NCIs and IMCs will be recorded.
- ⁿ A single blood sample will be collected for biobanking at the beginning of the study (prior to dosing on Day 1) and end of the study. This sample will be used for future analyses not specified in the protocol. Analysis will be limited to HBV serologic and HBV-specific DNA and RNA and patients' DNA will not be analyzed.
- ° Safety laboratory testing, including liver panel, for Doses 1 and 2 will be obtained during the visits conducted 7±2 days after these doses of study medication. Safety laboratory testing following Doses 3, 4 and 5 will be obtained in the interval from 7 days after dose administration and before the next dose of study medication is administered. Safety labs after Dose 6 will be assessed at the Day 169 visit.
- ^p Diaries will also be reviewed at the Day 85, Day 113, Day 141 and Day 169 visits

Table 2 Schedule of Events – Follow-up Period

	Follow-Up Period					
Study Visit	Day 232	Day 323	Day 414	Day 505 or ET ^a		
Completion of Week (number)	33	46	59	72		
Window (days)	±10 days	±10 days	±10 days	±10 days		
Visit may be conducted at home or work or in part as a telemedicine visit ^b	X		X			
Immunosuppressive medications, vaccines, and new HBV treatments (only) ^c	X	X	X	X		
Targeted and symptom-driven PE	X	X	X	X		
Height and weight				X		
Vital signs ^d	X	X	X	X		
ECG ^d				X		
Hematology and serum chemistry	X	X	X	X		
Liver panel	X	X	X	X		
HBV serology and viral markers ^e		X		X		
Whole blood for PBMC isolation		X		X		
MAEs, NCIs and IMCs (only) ^f	X	X	X	X		

AE = adverse event; ECG = electrocardiogram; ET = early termination; HBV = hepatitis B virus; HIV = human immunodeficiency virus; MAE = medically-attended adverse event; NCI = new-onset chronic illness; IMC = immune-mediated medical condition; PBMC = peripheral blood nonnuclear cell; PE = physical examination.

^a If a patient prematurely discontinues study medication before Day 505, Day 505/Early termination procedures will be performed.

^b A telemedicine visit would include a home visit by appropriate trained personnel to perform a target and symptom-driven physical and obtain vital signs and safety laboratories. The remaining portions of the visit may be conducted virtually by the study investigator.

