Safety endpoints that are also measured during the Follow-Up period will be assessed separately for the 24-week Treatment Period and 52-week Follow-Up Period.

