5.3.9 Missing Data and Outliers

5.3.9.1 Missing data

A missing data point for a given study visit may be due to any one of the following reasons:

- The visit did not occur
- The visit occurred but data were not collected or were unusable
- The patient permanently discontinued from the study before reaching the window for the study visit

In general, missing baseline data will not be imputed. The following approaches are default methods for missing data handling in summary tables:

- Categorical data at baseline will be summarized for each treatment arm using counts (n) and percentages (%). Unless otherwise specified, denominators for all percentages will be the total number of patients in the corresponding treatment arm and dose number (if applicable) within the population of interest.
- Continuous data: The analyses and summaries for variables with continuous scales will be based on observed data only. Only available data will be used.
- In general, change from baseline is calculated only for patients with non-missing values for both the baseline and the time-point of interest and will be missing otherwise.

Missing data commonly encountered during the study may comprise:

- Missing/Partial Dates: For incomplete days or months, an imputation will be done by assigning the first day of month or the first month of year, respectively. For incomplete years in dates for measurements after randomization, the year of first dose date will be assigned.
- Continuous variables: mixed models are robust to the presence of missing at random and conducts the analysis with all participants despite the presence of missingness. Of note, this method calculates the estimations based on the variance-covariance structure but without any formal imputations.

Missing data commonly encountered for safety and background variables may comprise:

- Missing/Partial Dates for AEs:

Missing or partial AE onset dates and times will be imputed so that if the partial AE onset date/time information does not indicate that the AE started prior to treatment or after the TEAE

period, the AE will be classified as treatment-emergent. These data imputations are for categorization purpose only and will not be used in listings. No imputation is planned for date/time of AE resolution.

Missing/Partial Dates for Concomitant Medications:

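### The TEAE definition has no end date; read literally, the main AE tables would mix fully collected treatment-period events with selectively collected follow-up events

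*SAP*

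**What the plan says.** **Definition.** SAP 5.3.3.2: "A TEAE is defined as an AE that starts or worsens on or after the date and time of the first administration". No end is given.

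**An end is assumed elsewhere.** The rule for incomplete onset dates in the same section classes an event as treatment-emergent "unless there is definitive information to determine it is pre-treatment or post-treatment". SAP 5.3.9.1 does the same where the partial date "information does not indicate that the AE started prior to treatment or after the TEAE" period. Neither the post-treatment category nor the TEAE period is given a length.

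**Period rule.** Protocol 3.4: "Safety endpoints will be assessed separately for the 24-week Treatment Period and 52-week Follow-Up Period". SAP 4.3: "Safety endpoints that are also measured during the Follow-Up period will be assessed separately for the 24-week Treatment Period and 52-week Follow-Up Period". Incidence and severity of AEs is the first endpoint on both lists.

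**Recording.** Protocol Table 1, footnote m: "After Day 169 or ET, only MAEs, NCIs and IMCs will be recorded". Protocol 4.1 and SAP 2.3 class these later events as AEs.

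**Data cut.** Protocol 10.5 locks the database first when all patients have completed Day 169 or left the trial, and reports efficacy and safety on everything accrued by then.

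**Tables.** SAP 5.3.3.4 to 5.3.3.6 split MAEs, NCIs and IMCs by period. SAP 5.3.3.2 and 5.3.3.3 do not split the TEAE, related-TEAE, severity or serious-TEAE summaries, and the titles of Tables 14.3.1.1 to 14.3.1.6 and 14.3.2.1 name no period. The overview also has an MAE row with no period.

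**The concern.** A programmer who follows 5.3.3.2 and the table index as written would count every recorded AE after first dose, however late. Up to Day 169 or ET that means all AEs. Afterwards it means only MAEs, NCIs and IMCs. At the first lock, early enrollees may have most or all of their follow-up behind them, while the last enrollee has none.

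The resulting percentages would combine two recording regimes and unequal follow-up. They would not estimate the 24-week incidence that Protocol 3.4 calls for, nor the incidence over any common period. Follow-up MAEs, NCIs and IMCs would be counted in the TEAE tables and again in the follow-up tables. The MAE row of the overview would match neither of the two MAE tables. These are the main AE tables behind the SAP's statement that the product was well tolerated. Without an end date, the partial-date rule in 5.3.9.1 cannot be programmed either.

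**Working it through.** **1. Timeline.** Inputs: last dose Day 141 (SAP 2.3.3), 52 weeks of follow-up after it, and 504 days beyond Day 1 (SAP 2.3).
- 141 + 52 × 7 = 141 + 364 = Day 505.
- 505 − 1 = 504 days beyond Day 1, as stated.
- 5 + 20 + 52 = 77 weeks, as stated.

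**2. What an open window covers in a completer.**
- Full recording: 169 − 1 = 168 days after Day 1.
- Restricted recording: 505 − 169 = 336 days.
- Restricted share of the open window: 336 / 504 = 66.7%.

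With the window closed at Day 169 or ET, all of it is under full recording.

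**3. Does the Week 24 lock remove the problem?** No. The lock waits for the last patient's Day 169 and does not truncate data at each patient's own Day 169. To illustrate, assume uniform accrual over E days, no dropout, and a lock at the last patient's Day 169. Time from a patient's Day 169 to the lock is then u, uniform on (0, E), and accrued restricted time is min(u, 336). For E above 336 its mean is 336 − 336² / (2E), where 336² = 112,896.

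| Accrual | E (days) | Mean restricted days | Share of time after Day 1 |
|---|---|---|---|
| 24 months (planned) | 730 | 336 − 112,896/1,460 = 258.7 | 258.7 / (258.7 + 168) = 60.6% |
| 18 months | 547 | 336 − 112,896/1,094 = 232.8 | 232.8 / (232.8 + 168) = 58.1% |
| 12 months | 365 | 336 − 112,896/730 = 181.3 | 181.3 / (181.3 + 168) = 51.9% |

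The planned 24 months is from Protocol 5.1; the shorter periods are a sensitivity range. These are shares of person-time. The tables report the number and percentage of patients, so the shares do not convert into a change in any percentage. The documents give no event counts from which to work that out.

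**4. Which tables are exposed.**
- 14.3.1.1 to 14.3.1.6: exposed to both the mixed recording and the unequal follow-up.
- 14.3.2.1 (serious TEAEs): less exposed to the first. An AE leading to hospitalization or an emergency visit is an MAE (Protocol 9.1.4) and is recorded in both periods. Unequal follow-up remains.
- 14.3.2.2 (TEAEs leading to permanent discontinuation): barely exposed. The last dose is on Day 141, so in a completer an event after Day 169 can hardly lead to withdrawal of the drug.

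**The case against.** The strongest reply is that the SAP, read as a whole, intends a bounded window. Section 5.3.3 refers safety endpoints back to Section 4.3, which contains the period split. Section 5.3.3.2 treats post-treatment events as not treatment-emergent, and 5.3.9.1 speaks of a TEAE period. The addendum does not list the main TEAE tables for regeneration with later follow-up; it adds only follow-up MAE, NCI and IMC tables and listings. The AE listing flags which events are treatment-emergent.

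Much of this stands. A reader might infer that the tables did pool the two periods; the documents do not show that. Pooling is what the definition would produce if programmed literally. But an intention with no date is not a rule that can be programmed, and the only operative definition conflicts with Section 4.3. The addendum does not settle it, because early enrollees' follow-up events could already be in the database at the Week 24 lock.

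A reader might also take the missing Through D169 mark on the TEAE tables in Appendix 1 as proof that follow-up data were meant to be included. It is weak evidence. The urinalysis, hepatitis-flare and concomitant-medication tables are limited to the treatment period by the SAP text and also lack the mark.

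Finally, closing the window without other changes would lose information. The follow-up tables show MAEs, NCIs and IMCs by system organ class and preferred term only, so seriousness, relatedness and severity in follow-up would remain only in listings. That objection is sound, and the fix must meet it.

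**Conclusion.** The point holds as an undefined end to the TEAE period and a conflict between SAP 5.3.3.2 with its table index, on one side, and SAP 4.3 and Protocol 3.4 on the other. It should be corrected. Taken literally, and given a lock that reports all accrued data, the main TEAE tables would yield percentages without a clear time frame.

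The size of the effect on those percentages is unknown. The 52 to 61% of person-time rests on assumed uniform accrual, no dropout and the assumed lock date. It shows only that the first lock does not make the problem negligible by design. A reader might go further and infer biased safety comparisons between arms. That is not supported, because both arms share the same definition and recording rule. Efficacy is unaffected.

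**What to change.** - In SAP 5.3.3.2, define a TEAE as an AE with onset or worsening from first dose through Day 169 or ET from the Treatment Period. This matches the end of full AE recording. A fixed span to Day 169 for early stoppers would not, because their recording is already restricted after ET.
- Use the same end for the post-treatment category in 5.3.3.2 and for the TEAE period in 5.3.9.1.
- Apply the filter to Tables 14.3.1.x and 14.3.2.x, including the MAE row of the overview, and name the period in their titles.
- Report later onsets in the Follow-Up Period MAE, NCI and IMC tables. Add follow-up counts of serious, related and severe events, or point explicitly to the listings that carry them.
- Confirm whether the Week 24 tables excluded onsets after each patient's Day 169 or ET. If they did not, rerun them with the filter or footnote the clinical study report.

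The cost is a short SAP clarification, minor reprogramming and a few extra follow-up rows. No new data are needed.
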